### ***11.3.2 Secondary and Exploratory Endpoint Analysis***

The secondary endpoints are change from baseline in the (a) Average Trichogram growth rates at 24 weeks, (b) Average Trichogram density rate at 24 weeks, and (c) global photographs at 24 weeks and (d) hair Investigator Satisfaction Survey at 24 weeks. Multiplicity adjustment will not be made when testing the three secondary endpoints.

Exploratory endpoints are listed in [Section 4.5](#). As these are exploratory, p-values for each analysis will not be corrected for multiple comparisons. These analyses will provide evidence concerning the safety of effectiveness of the product.

### ***11.3.3 Subgroup Analysis***

Statistical analysis of efficacy and safety endpoints will be performed in the total group.

## **11.4 Background, Demographic Analyses**

Demographic data, medical history, concomitant disease will be summarized by means of descriptive statistics (n, mean, SD, median, minimum and maximum) or frequency tables, stratified by treatment.

## **11.5 Subject Disposition & Analysis Populations**

Reasons for withdrawal post-randomization will be summarized.

The treatment analyses will be performed on intent-to-treat basis as well as on a per-treatment-evaluable basis, as defined below:

Safety: All treated subjects; subjects will be analyzed as treated.

Intent-to-Treat (ITT): All randomized subjects; randomization will occur on procedure day prior to liposuction. Subjects will be included in the analysis as randomized

Per-Treatment-Evaluable (PTE): All randomized subjects who have received treatment and follow-up information is available. Protocol violators, where the violation is judged to affect the interpretation of the treatment effect will be excluded. All exclusions will be made prior to the breaking of the treatment blind.

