### Autologous Fat Transfer

In an AFT procedure, a patient's subcutaneous adipose tissue is aspirated from one location (most commonly the abdomen or thighs) and transferred into another depot of subcutaneous fat located throughout the body (e.g., mid-face). This procedure is reported to be practiced by physicians for over 100 years and autologous fat should be free from problems often associated with artificial materials or from allergic reactions. However, AFT is not without its own limitations most significant of which is the fact that an unpredictable amount of the transferred fat can die as a result of damage during tissue harvest, processing, and implantation leading to loss of volume and a degree of unpredictability in outcome.

The process of fat transfer necessarily involves disconnecting the fat from its blood supply, implanting it into the defect, and then waiting for natural healing processes to incorporate the transferred tissue with native fat. Survival of the transferred tissue is dependent upon harvest and processing approaches that maximize tissue viability. It is also dependent upon simple diffusion to supply nutrients and oxygen and to remove wastes until such time as healing processes restore its blood supply. Diffusion through a solid tissue such as fat is only effective across a distance of a few millimeters. Consequently, any transferred tissue that is more than a few millimeters away from the blood supply of recipient site tissue is at risk of dying. Loss of graft tissue from this problem is a frequent problem. Clinicians frequently overcorrect adding extra tissue in an effort to compensate for inevitable tissue loss that has been estimated at between 20-80% of the implanted tissue. As a result of this unpredictability defect repair frequently requires multiple repeated or staged procedures performed at intervals of three or more months. For example, one large study reports up to five treatments needed (mean = three treatments) in order to achieve success in restoring volume. This leads to delays in achievement of effective treatment of the defect, expense, and the higher morbidity of repeated tissue collection and implantation.

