### 5.2 Randomization and Subject Identification

All subjects will undergo liposuction and will be randomized into one of four parallel arms in a 2:2:2:1 ratio to receive either low dose ADRCs cell enriched fat (n=20), high dose ADRC cell enriched fat (n=20), non-cell enriched autologous fat alone control (n=20), or no-fat control saline injections (n=10). Randomization will be via an interactive voice/web response system (IVRS/IWRS), or an alternatively acceptable system, and occur on the procedure day, prior to the start of liposuction.

Patients randomized into the study will be assigned the treatment corresponding to the next available number in the computer-generated randomization schedule. The dose of the test material (ADRCs or placebo) is discussed in [Section 6.3](#).

Randomization and dose preparation will be performed by an unblinded pharmacist, or other designated qualified personnel, as outlined in the Study Reference Manual. The unblinded pharmacist or designee will not be involved in study patient care, management or follow up procedures and assessments.

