## 7 STUDY TREATMENTS

Subjects will be randomized 2:2:2:1 to active treatment (autologous fat enriched with ADRCs), autologous fat alone control, or no-fat control as follows:

Active ( $0.5 \times 10^6$ ADRCs/cm  scalp):	20 Subjects
Active ( $1.0 \times 10^6$ ADRCs/cm  scalp):	20 Subjects
Autologous fat alone control:	20 Subjects
No-fat control (saline)	10 Subjects

The study treatment will be administered as subcutaneous injections of either fat or saline into the subcutaneous fat layer of the scalp (40cm^2 of scalp) of each subject. Each square centimeter of scalp will be injected with 0.1 mL of purified autologous fat or saline followed by separate injection of either low or high dose ADRC injection per cm^2 scalp, or saline (fat alone control and the no-fat control). To account for the variability seen in advanced grades of hair loss (Norwood Grade II and IV), treatment areas will be focused in the mid-scalp and crown (vertex). The leading edge of hair loss will not be treated, including the peri-orbital region as fat grafting in the peri-orbital region has been associated with higher-risk complications.

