## **11 STATISTICAL METHODS AND DATA ANALYSIS**

This is a multi-centre, single-blinded, randomized, parallel group, controlled study to evaluate the preliminary safety of cell-enriched autologous fat compared to placebo in patients with baldness due to alopecia androgenetica. The primary endpoint will be the safety and tolerability of the procedure.

An analysis of covariance (ANCOVA), with the baseline measure used as a covariate, will be used for the analyses of the secondary efficacy endpoints. Comparisons of each active arm with placebo will be made using Dunnett comparisons. The ITT population will be used for the primary analysis; the analysis will also be performed in the PTE population and will be considered as supportive of the ITT analysis.

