### **11.3 Data Analyses**

Safety and efficacy endpoints will be summarized by treatment group using descriptive statistics (n, mean, SD, median, minimum, and maximum), for quantitative variables and frequencies and percentages for categorical variables. Laboratory data will also be summarized using shift tables

between before procedure and at Day 1, post procedure, with values categorized as less than lower limit of normal range, within normal range, and above upper limit of normal range.

For quantitative efficacy variables, summaries will be provided at each post-baseline visit time point. Additionally variables will be analyzed using ANCOVA models with adjustment for the baseline value of the variable.

Related adverse events will be analyzed separately for those related to ADRCs and the delivery of ADRCs (i.e., injection site such as shock loss). A separate safety analysis will be performed for Adverse Events of Interest ([Appendix B, Adverse Event Terminology and Grading](#)).

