### ***11.3.1 Primary Endpoint Analysis***

The primary endpoint for the study is safety and tolerability through 24 weeks

The hypotheses are:

Adverse event rates through 24 weeks for active treatment will be less than or equal to adverse events rates published for autologous fat grafting.

Vital sign abnormalities through 24 weeks for active treatment will be less than or equal to those published for autologous fat grafting.

Physical exam abnormalities through 24 weeks for active treatment will be less than or equal to those published for autologous fat grafting.

The corresponding null hypotheses are that the adverse event rates will be greater for active treatment arms than for placebo.

Statistical testing will not be performed for these hypotheses, but the safety endpoints will be evaluated clinically.

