## APPENDIX B: ADVERSE EVENT TERMINOLOGY AND GRADING

(Adapted from National Cancer Institute Common Terminology Criteria for Adverse Events)

Adverse Event	Short Name	Severity Grading				
		1	2	3	4	5
Bruising (in absence of Grade 3 or 4 thrombocytopenia)	Bruising	Localized or in a dependent area	Generalized	-	-	-
Hyperpigmentation	Hyperpigmentation	Slight or localized	Marked or generalized	-	-	-
Hypopigmentation	Hypopigmentation	Slight or localized	Marked or generalized	-	-	-
Injection site reaction/extravasation changes	Injection site reaction	Pain; itching; erythema	Pain or swelling, with inflammation or phlebitis	Ulceration or necrosis that is severe; operative intervention indicated	-	-
Hematoma	Hematoma	Minimal symptoms, invasive intervention not indicated	Minimally invasive evacuation or aspiration indicated	Transfusion, interventional radiology, or operative intervention indicated	Life-threatening consequences; major urgent intervention indicated	Death
Hemorrhage/bleeding associated with surgery, intra-operative or postoperative	Hemorrhage with surgery	-	-	Requiring transfusion of 2 units non-autologous pRBCs beyond protocol specification; postoperative interventional radiology, endoscopic, or operative intervention indicated	Life-threatening consequences	Death

Adverse Event	Short Name	Severity Grading				
		1	2	3	4	5
Infection with normal ANC or Grade 1 or 2 Neutrophils at the site of liposuction or cell-enriched injection	Infection with normal ANC at the site of liposuction or ADRC injection	-	Localized, local intervention indicated	IV antibiotic, antifungal, or antiviral intervention indicated; interventional radiology or operative intervention indicated	Life-threatening consequences (e.g., septic shock, hypotension, acidosis, necrosis)	Death
Pain at the site of liposuction or cell-enriched injection	Pain	Mild pain not interfering with function	Moderate pain; pain or analgesics interfering with function, but not interfering with ADL	Severe pain; pain or analgesics severely interfering with ADL	Disabling	-

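### Two passages file adverse events before the injection as medical history, against Section 12.2, and the Safety set as worded would leave out a subject stopped at harvest

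*Combined protocol and SAP*

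**What the plan says.** All references are to Protocol Version B.

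Section 11 states: "The primary endpoint will be the safety and tolerability of the procedure". Section 11.3.1 sets the first safety hypothesis: "Adverse event rates through 24 weeks for active treatment will be less than or equal to adverse events rates published for autologous fat grafting". It plans no statistical test; the safety results are judged clinically. Section 11.3 adds: "A separate safety analysis will be performed for Adverse Events of Interest". Those events are graded in Appendix B, which includes "Pain at the site of liposuction or cell-enriched injection", infection at the liposuction site and intra-operative bleeding.

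On AE recording, Section 8.1 and the second sentence of Section 8.5 place events between consent and the giving of the study drug in medical history. The first sentence of 8.5 starts AE recording on Day 1 once the study procedure has begun. Section 12.2 uses the AE eCRF from the start of liposuction-related activities, and footnote 1 of Appendix A makes the same cut.

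On the analysis set, Section 11.5 says only "Safety: All treated subjects; subjects will be analyzed as treated". Randomization is to "occur on the procedure day, prior to the start of liposuction" (Section 5.2). Section 7 describes what is given: "The study treatment will be administered as subcutaneous injections of either fat or saline into the subcutaneous fat layer of the scalp". Section 9.3.1.3 lists harvest complications that end the harvest, bar injection and require an SAE form.

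**The concern.** The primary conclusion rests on tabulated AE counts, with no test behind them. Two pieces of wording decide which events reach those tables, and both are loose at the harvest.

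The filing rule is the more important. Harvest comes before injection, so a rule that files pre-administration events as background takes in anything that arises during liposuction, including in subjects who go on to be injected. It needs no rare complication to operate.

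The set definition matters only if a harvest is stopped. The subject has been randomized, has had part of a procedure whose safety is the endpoint, and has had one of the more serious harvest harms the protocol names, yet may not count as treated.

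**Working it through.** **1. Filing of a harvest AE, texts side by side**

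| Place | Cut-point | A harvest AE goes to |
|---|---|---|
| 8.1 | giving of the study drug | medical history |
| 8.5, second sentence | giving of the study drug | medical history |
| 8.5, first sentence | start of the study procedure, Day 1 | AE record, if the procedure includes liposuction |
| 12.2 | start of liposuction-related activities | AE eCRF |
| Appendix A, footnote 1 | start of liposuction-related activities | not medical history |

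The term *study drug* is not defined in this device trial. The natural reading is the scalp injections, which follow the harvest (Section 9.3.3, Appendix C). As the columns of Appendix C read, liposuction is at Hour 0, the fat or saline injection at Hour 1 and the cell or saline injection at Hour 4. The exposed window is therefore about one hour, or about four if the term means the cell injection. Events with onset after injection are not affected. The documents give no AE rate for this window, so no count can be attached.

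**2. Membership of the Safety set**

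- Randomization precedes liposuction (5.2), so a subject stopped at harvest is in the ITT set.
- A listed complication bars injection (9.3.1.3).
- Section 7 equates study treatment with the scalp injections. Section 7.2.1 lists harvest and injection as separate steps. Section 7.1.1 calls a harvested subject with failed cell viability not treated. Section 7.3 says a subject with a positive Gram stain should get no study treatment.
- On that usage, the stopped subject is randomized but not treated: in ITT, outside Safety.

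**3. Scale of point 2**

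Allocation first: 70 × 2/7 = 20 and 70 × 1/7 = 10, which agrees with the plan's 20/20/20/10.

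Suppose one stopped subject (an assumed count). Exact Clopper-Pearson 95% limits follow. With no events in n subjects, the upper limit is 1 − 0.025^(1/n).

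| Group | Counted | Left out |
|---|---|---|
| All subjects | 1/70 = 1.4% (0.04 to 7.7) | 0/69, upper limit 1 − 0.025^(1/69) = 5.2% |
| Both cell arms | 1/40 = 2.5% (0.06 to 13.2) | 0/39, upper limit 9.0% |
| One arm of 20 | 1/20 = 5.0% (0.13 to 24.9) | 0/19, upper limit 1 − 0.025^(1/19) = 17.6% |
| No-fat arm | 1/10 = 10.0% (0.25 to 44.5) | 0/9, upper limit 33.6% |

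The chance of at least one such subject among 70 is 1 − (1 − p)^70. The stop rate p is an assumption:

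- p = 0.1%: about 7%
- p = 0.5%: 29.6%
- p = 1%: 50.5%
- p = 2%: 75.7%

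The intervals overlap in every row. What changes is whether one serious event shows in a table, not whether a difference in rates could be detected.

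**The case against.** A reader might infer that harvest harms disappear from the trial, or that the Safety set tilts the comparison towards active treatment. The documents support neither. A stopping event goes on an SAE form and to the sponsor (9.3.1.3), and under 12.2 on the AE eCRF. The DMC receives all safety data (11.8), and reasons for withdrawal after randomization are summarized (11.5). All arms have liposuction, so harvest stops should not differ by arm.

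On filing, Appendix A collects medical history only before the procedure and on Day -1, and its AE row begins on Day 1. Section 8.5 also refers the reader to Section 12. Misfiling is thus less likely than the two sentences suggest. This stands as mitigation, but it does not remove a written rule that says the opposite.

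On the set, Section 9.3.1.1 calls the liposuction independent and elective, so a set restricted to injected subjects is defensible. The benchmark gives some support to that view. The protocol describes fat transfer as tissue that is first taken, "subcutaneous adipose tissue is aspirated from one location", and then transferred; a harvest-only subject had no transfer and no active treatment. Whether the published rates count aborted harvests cannot be told from the documents. Against this, the endpoint is the safety of the procedure, and Appendix B grades liposuction-site events. The sensible answer is to report both.

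Usage of *treated* is also not uniform. Appendix C shows the first injection while cell processing and the Gram stain are still under way, so a subject failing viability could be treated under Section 7 and not treated under 7.1.1. The separate SAP announced in Section 11.1 is not among the documents and may define the word. Finally, the stop rates above have no source, and Section 10.1.5 calls the risks of small-volume liposuction minimal.

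Section 11 does name ITT for the primary analysis, which might seem to keep the stopped subject in. That sentence belongs to the paragraph on the efficacy ANCOVA, and 11.5 gives safety its own set.

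**Conclusion.** The filing rule is wrong as written. Two statements, if followed, take harvest AEs out of the primary safety endpoint, and three others say the reverse. The weight of the text favours 12.2, so this is a contradiction to remove, not an established loss of data. Its size cannot be computed from the documents.

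The Safety-set point holds in a smaller form. It rests on how the protocol mostly uses *treated*, not on a definition. One stopped subject would move the table entry from 1/70 to 0/69 overall, or from 1/20 to 0/19 in one arm. The event would still be known to the sponsor and the DMC. There is no effect if no harvest is stopped. Both points are worth correcting because the primary endpoint is read from counts and the correction is cheap.

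**What to change.** - Align 8.1 and the second sentence of 8.5 with 12.2 and footnote 1 of Appendix A, and replace the undefined term *study drug*.
- In 11.5 and the SAP, define the Safety set as all randomized subjects in whom liposuction-related activities were started. This is the cut-point that 12.2 already uses.
- Show uninjected and partly injected subjects separately, with reasons, AEs and length of follow-up, and state in advance the column in which they appear.
- Report AEs for injected subjects as well, since the liposuction is described as independent and the published benchmark may not count aborted harvests.

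The cost is wording in two documents. Follow-up visits are titled as post-injection, so uninjected subjects may have only the early termination evaluation (9.7), and their shorter follow-up must be visible. The reported AE rate may be slightly higher.

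Two neighbouring inconsistencies are separate and also need reconciling: Week 24 (8.5) against Week 52 (9.6, Appendix A) as the end of AE recording, and the order of the first injection and the release tests (7.1.1, 7.3, Appendix C). No clinical rule is proposed for either.

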### **7.1.1 Active Treatment Dose Control**

Autologous adipose purified with the Puregraft System can be readily removed directly with a sterile 1mL syringe to obtain a volume of 0.1mL for injection.

ADRC Cell count and viability will be controlled using the NucleoCounter Automated Cell Counting System (Enfield, CT) at each site using the following acceptance criteria:

- Nominal cell count:  $40 \times 10^6$  ADRCs
- A minimum cell count within 50% of the nominal cell count is required (i.e., a dose as low as  $20 \times 10^6$  ADRCs is acceptable if  $40 \times 10^6$  ADRCs is not available)
- Cell viability:  $\geq 70\%$   
If cell viability is  $<70\%$ , as determined by the NucleoCounter Automated Cell Counting System, the subject will not be treated.
- Negative result in Gram stain testing (see [Section 7.3](#))

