#### ***9.3.1.3 – Fat Harvest Stopping Rules***

The physician performing the fat harvest procedure should continuously monitor the patient for signs of significant bleeding from the puncture site(s) and overall hemodynamic stability. The liposuction procedure should be terminated if any of the following occur:

1. Drop in systolic blood pressure < 90mm/Hg that is unresponsive to volume or pressor support
2. Profuse or uncontrollable bleeding from the puncture site(s)
3. Rapid expansion of subcutaneous space at the liposuction site(s) related to bleeding into the subcutaneous space
4. Hemoperitoneum or pneumoperitoneum
5. Hemothorax or pneumothorax
6. Evidence of perforation of a vascular structure that requires ligature or surgical control

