## 7. Evidence of perforation into abdominal cavity, peritoneum or gastrointestinal organ

Should any of the above occur, the fat harvest procedure should be terminated and the patient treated according to standard of care. DO NOT PROCEED WITH INJECTION. Complete the study specific SAE form and notify the sponsor within 24 hours.

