#### Autologous Fat & Saline Injection

This fat or saline injection procedure will occur after the completion of the liposuction. Aseptic technique should be maintained throughout the procedure. A treatment grid will be prepared in the area to be treated. The grid is a piece of silicone rubber that is placed on the scalp of the subject in the desired position and a surgical skin marker is used to mark each of the holes which are spaced every centimeter. The recipient site is anesthetized using a local ring block with 1% lidocaine with 1:100,000 epinephrine. Aliquots of 0.2mL should be injected in a circular ring fashion and the dosage should be adjusted according to the response of the patient and the site of administration. The lowest concentration and the smallest dose producing the required effect should be given. The maximum dose delivered should not exceed 7mg/kg. Sedation may be employed to minimize patient discomfort at the discretion of the investigator. Tissue from the Puregraft 50 is prepared in separate, sterile 1mL luer lock syringes, and an 11-blade scalpel can be used to make a stab incision (incision is made at a strategic insertion point to facilitate access to the area to be treated) to allow insertion of a 0.9mm-1.2mm diameter blunt-tip cannula. This cannula is then inserted into the subcutaneous adipose tissue plane and the tip is fanned into each 1 square centimeter grid to deliver 0.1mL of tissue or saline (no-fat control).

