## **12.2 Procedures for AE Reporting**

All AEs will be recorded by the investigator or designee on the appropriate electronic case report form (eCRF). Events that occur prior to the liposuction-related activities, including those that are considered serious, are to be recorded in the medical history. Events, including SAEs, which occur after liposuction-related activities are initiated on procedure day, are to be recorded on the AE eCRF. The investigator will evaluate the relationship of the adverse event to both the test material and study procedure as unrelated, unlikely, possibly, probably, or definitely related and will record the findings, including all pertinent details of the event on the eCRF.

In addition, the Investigator or designee will report any serious adverse events, including UADE, occurring during this study to the Sponsor and Medical Monitor as soon as possible, but no later than 24 hours after the Investigator first identifies the adverse event.

The Investigator will take appropriate measures to ensure the subject's well-being and document these measures on the appropriate eCRF.

All serious adverse events experienced will be monitored until the event has resolved, any abnormal laboratory values have returned to baseline or stabilized at a level acceptable to the Investigator and Medical Monitor, or until there is a satisfactory explanation for the changes observed.

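### The Safety population in Section 11.5 is tied to treatment, so a randomized subject whose fat harvest is stopped for a serious event appears to fall outside it

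*Combined protocol and SAP*

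**What the plan says.** All references are to Protocol Rev B, the current version.

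- **Randomization.** Sections 5.2 and 11.5 place it on the procedure day, before liposuction. ITT is everyone randomized.
- **Recording of events.** Section 12.2 says that events, SAEs included, "which occur after liposuction-related activities are initiated on procedure day, are to be recorded on the AE eCRF".
- **Stopping the harvest.** Section 9.3.1.3 lists seven reasons to end the liposuction, among them uncontrolled bleeding at the puncture sites, haemothorax and perforation of the abdominal cavity. The instruction is then "DO NOT PROCEED WITH INJECTION", with an SAE form and notice to the sponsor within 24 hours.
- **What treatment is.** Section 7: "The study treatment will be administered as subcutaneous injections of either fat or saline". Section 9.3.3: "This fat or saline injection procedure will occur after the completion of the liposuction".
- **Safety population.** Section 11.5: "Safety: All treated subjects; subjects will be analyzed as treated". The PTE population also requires that treatment was received.
- **Primary endpoint.** Section 11: "The primary endpoint will be the safety and tolerability of the procedure". Section 11.3.1 plans no test; safety is judged clinically.
- **Events of interest.** Section 11.3 plans a separate analysis of the Appendix B events. Appendix B includes intra-operative haemorrhage, and also pain and infection at the liposuction site.

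**The concern.** The window for recording adverse events opens at liposuction, but the population for summarizing them appears to open at injection. Between the two lies the part of the day in which the gravest surgical complications would occur, and those complications are what prevent the injection. Membership of the Safety population therefore depends on not having had such an event.

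This matters because no hypothesis test is planned. The clinical reading of the tabulated rates is the primary analysis. Appendix B also shows that the sponsor wants harvest-site events analysed, so leaving out the worst of them is probably not intended.

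**Working it through.** **1. Follow one stopped subject through the text.**

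| Step | Section | Status of the subject |
|---|---|---|
| Randomized before liposuction | 5.2, 11.5 | In ITT |
| Liposuction starts | 12.2 | Events go on the AE form |
| Stopping rule met | 9.3.1.3 | SAE form; no injection |
| First scalp injection would follow completed liposuction | 9.3.3 | Never reached |
| Study treatment is the scalp injections | 7 | None received |
| Safety is treated subjects, as treated | 11.5 | Not in Safety; no arm to be placed in |
| PTE requires treatment | 11.5 | Not in PTE |

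The protocol does not formally define the word treated. The reading rests on Section 7, supported by Section 9.3.1.1, which describes the harvest as part of a separate elective cosmetic procedure.

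**2. Is a population named for the safety tables?** Section 11.3 says only that summaries are by treatment group. Section 11.3.1 names no population. Section 11.3.3 refers to the total group, but in the sense of no subgroups. Section 11.1 leaves detail to a separate SAP, which is not among the documents.

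**3. Is the recording rule itself clear?** Section 12.2 and footnote 1 of Appendix A agree that events go to medical history only if they precede liposuction-related activities. Sections 8.1 and 8.5, however, send events before administration of the study drug to medical history. A stopped-harvest event precedes any administration, so those two sections conflict with Section 12.2 for exactly this subject.

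**4. Size.** The plan gives no rate for harvest stops and no related figure to reproduce. The counts *k* below are assumptions. They suppose that all 70 planned subjects (20 + 20 + 20 + 10) start liposuction, everyone else is injected, and no injected subject has such an event. Limits are exact (Clopper-Pearson) 95% upper limits. For 0/n the limit is 1 − 0.025^(1/n); for n = 69 this is 1 − 0.025^(1/69) = 5.2%.

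| Stops *k* | Liposuction started: *k*/70 (upper limit) | Treated only: 0/(70 − *k*) (upper limit) |
|---|---|---|
| 1 | 1.4% (7.7%) | 0/69 (5.2%) |
| 2 | 2.9% (9.9%) | 0/68 (5.3%) |
| 3 | 4.3% (12.0%) | 0/67 (5.4%) |

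The chance of at least one stop among 70 is 1 − (1 − p)^70. For assumed true rates p of 0.1%, 0.5%, 1% and 2% it is 6.8%, 29.6%, 50.5% and 75.7%.

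**The case against.** **ITT may govern safety.** Section 11 calls safety the primary endpoint and then says that ITT is used for the primary analysis. ITT would include the stopped subject. But that sentence closes the paragraph on ANCOVA and Dunnett comparisons and goes on to PTE as supportive. If ITT governed safety, a separate Safety definition would have no use. The text is ambiguous enough that exclusion is not certain, but it does not repair the definition.

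**Section 7.1.1 does not settle the meaning of treated.** It says of low cell viability that "the subject will not be treated", which a reader might take as proof that harvested subjects count as untreated. Appendix C places the fat or saline injection at Hour 1, ahead of the ADRC injection, while ADRC processing is still to finish. Such a subject may already have received fat, so the phrase may refer to the cells alone. This point does not rely on it. A stopped-harvest subject has received neither injection.

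**Restricting safety to recipients of the product is common practice.** That is true, and it suits injection-site events. It suits less well an endpoint worded as the safety of the procedure, with recording from the start of liposuction.

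**The events are not lost.** This also stands. There is an SAE form within 24 hours, follow-up of SAEs to resolution (Section 12.2), a summary of withdrawal reasons (Section 11.5) and DMC review of all safety data (Section 11.8). None of these puts the event into a rate.

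**The events are extreme and may never happen.** Section 10.1.5 lists bleeding that needs transfusion as rare. The size is therefore wholly conditional on the assumed counts.

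**Conclusion.** The gap is real and minor. On the protocol's own description of study treatment, a randomized subject with a serious harvest event is in ITT, outside Safety, and without an as-treated arm. If one such stop occurred, the harvest-stop rate would be 1.4% (upper limit 7.7%) among subjects harvested and 0/69 (upper limit 5.2%) among those treated. All arms have the same liposuction, so what changes is mainly the absolute procedure rate, not differences between arms.

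Three stronger readings are tempting but not supported:

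- *That these events drop out of every safety table.* No section assigns populations to tables, and the SAP may do so differently.
- *That the comparison with published fat-grafting rates in Section 11.3.1 is biased downward.* That hypothesis concerns active treatment, and the denominator of the published rates is not given. If those rates count only grafted patients, adding ungrafted subjects would make the comparison less like for like.
- *That haemoglobin and haematocrit values of stopped subjects are discarded.* Section 9.4 lists the test only after injection. Section 10.1.6 requires it 1 to 2 hours after the procedure, but a stopped subject moves to standard care, so the value may never be drawn. Section 11.3 does not tie the laboratory shift tables to a population either.

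**What to change.** In Section 11.5, define the Safety population as all randomized subjects in whom liposuction-related activities were started. This matches the recording rule in Section 12.2. In Section 11.3:

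- name this population for the adverse event, event-of-interest and laboratory summaries;
- show subjects harvested but not injected in their own column and in the overall total;
- keep injected subjects as the denominator for scalp injection-site events and for the active-treatment comparison with published rates;
- include post-harvest haemoglobin and haematocrit for uninjected subjects where they were drawn under Section 10.1.6.

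Sections 8.1 and 8.5 should be brought into line with Section 12.2, so that these events reach the AE form.

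The cost is a few sentences and one table column, with no added assessment. The drawback is that harvest events unrelated to ADRCs enter the overall rate; the separate column makes that visible.
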